10.3.2.2 Modified Full Analysis Set (mFAS)

Primary efficay analysis will be based on modified full analysis set (mFAS). Subjects who receive Hexvix instillation and undergo blue light cystoscopy, and are pathologically confirmed as Ta, T1, and CIS stage bladder cancer will be included in mFAS. Efficacy data of subjects who received Hexvix and white light cystoscopy but did not continue with blue light cystoscopy will not be included in mFAS. Training patients who receive Hexvix and white light cystoscopy and blue light cystoscopy and have evaluable data will not be included in mFAS.

10.3.3 Per Protocol Set

10.3.3.1 Per Protocol Set (PPS)

The analysis of secondary efficacy endpoints will be based on the per protocol set (PPS). PPS is a subset of FAS. A subject will be excluded from the PPS for the following reasons:

- Failure to fulfill inclusion criteria / exclusion criteria but still entered into the study.
- Failure to retain the Hexvix solution for at least 30 minutes.

Protocol violations that are thought to affect the result of the cystoscopy or the histologic result may result in subjects being excluded from the PPS (will be documented before data base lock).

10.3.3.2 Modified Per Protocol Set (mPPS)

The analysis of primary efficacy endpoints will be based on the modified per protocol set (mPPS). mPPS is a subset of mFAS. A subject will be excluded from the mPPS for the following reasons:

- Failure to fulfill inclusion criteria / exclusion criteria but still entered into the study.
- Failure to retain the Hexvix solution for at least 30 minutes.
- Subjects who protocol deviations that affected the evaluation of primary endpoint.

Protocol violations that are thought to affect the result of the cystoscopy or the histologic result may result in subjects being excluded from the mPPS (will be documented before data base lock).

The mPPS analysis is done as a supportive analysis of the primary efficacy endpoints, and will show if the exclusion of subjects from the mFAS will affect the overall conclusions of the results.

10.4 Statistical Analysis Method

10.4.1 Subject Disposion and Baseline Characteristic Analysis

All baseline and demographic data analysis will be performed on the basis of FAS and mFAS.

List the information of subjects who failed screening, including screening number and reasons for

Study Number: YHCT-HEX-B1

screening failure. Subjects who failed screening will be summarized, including number of screen failures, number of screen failures, and percentage of each screen failure reason.

The number of subjects enrolled in the study, the number/percentage of subjects undergoing white and blue light cystoscopy, the number/percentage of subjects included in the efficacy, safety evaluations, the number/percentage of subjects completing each period of the study, and the reasons for withdrawal will be summarized.

Listings of demographic data and baseline characteristics will be provided. Descriptive statistics will be performed for all demographic data and baseline characteristics (e.g., gender, age, ethnicity, height, weight, previous medical history, current medical history, medication history, urine cytology).

Details will be described in the statistical analysis plan.

10.4.2 Efficacy Ananlyses

Efficacy endpoint analysis will be based on FAS/mFAS and PPS/mPPS.

10.4.2.1 Primary Efficacy Endpoint

The analysis on primary efficacy endpoint will be performed on the basis of mFAS and mPPS. Primary efficacy endpoint will be analyzed based on subjects who received Hexvix instillation and continue with blue light cystoscopy, and are pathologically confirmed as Ta, T1, and CIS stage bladder cancer. Training patients will not be included.

For analysis of the primary efficacy endpoint (The proportion of patients with histology-confirmed tumors (Ta, T1, or CIS) who have at least one such tumor found by Hexvix but not by white light cystoscopy), an exact test for single proportion, using the cumulative binominal distribution, with a significance level of 0.025 (1-sided) will be used, based on the mFAS and mPPS, and the 95% confidence interval for the detection rate will be calculated.

10.4.2.2 Secondary Efficacy Endpoints

Secondary efficacy endpoints analysis will be based on FAS and PPS.

Secondary efficacy endpoints will be analyzed descriptively, including event rate and 95% confidence intervals based on the FAS and PPS. Exact 95% confidence interval will be calculated similarly to that of the primary efficacy endpoint. But no formal statistical inference will be made to the secondary efficacy endpoints.

If the establishment of confidence intervals is based on biopsy/TURBT data, Bladder biopsy/TURBT data should be assumed to be independent of each other.

Efficacy data will be tabulated in detail.

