2.2 Secondary Objective

- Comparison of detection of patients with CIS lesions by Hexvix blue light cystoscopy and white light cystoscopy.
- Comparison of detection rates of bladder lesions of Hexvix blue light cystoscopy and white light cystoscopy per lesion type (PUNLMP, CIS, Ta, T1, T2-4).
- Comparison of the proportion of false positive lesions detected with Hexvix blue light cystoscopy and white light cystoscopy.
- Evaluation of safety of Hexvix in patients with bladder cancer.

Version 2.2 Date: Feb 6th, 2023

Study Number: YHCT-HEX-B1

3. Selection and Withdrawal of Subjects

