In general, false fluorescence from normal tissue will be weak and diffuse. The endothelium of blood vessels and inflamed areas may show false fluorescence, but fluorescence from neoplastic lesions will be more intense and usually well demarcated. To avoid false fluorescence and get a brighter picture, the endoscope should be held perpendicular and close to the bladder wall. Tangential light will give false fluorescence. Changing of fluorescence intensity when varying the observation angle indicates false fluorescence, as true fluorescence is persistent. A brighter picture will be achieved using a low magnification if a zoom lens is used. Bleeding will reduce the image brightness and good irrigation should be used. Photo bleaching, which is caused by destruction of the photosensitizer and leads to reduced fluorescence intensity, should be kept at a minimum by avoiding unnecessary delay during inspection and mapping of the bladder. Photo bleaching is normally not a problem during inspection and mapping of the bladder, but may be noticed during extensive use of fluorescence-guided resection. However, regeneration of fluorescence may be seen in areas kept 'in the dark' for a few minutes. To minimize photobleaching, the use of white light should be performed under the lowest possible light intensity. Viewing conditions may be altered by the presence of urine, and the bladder should therefore

Study Number: YHCT-HEX-B1

be adequately evacuated before starting the procedure together with proper irrigation during the examination. Please ensure that the bladder is sufficiently distended as a folded bladder wall may result in increased fluorescence

4) Biopsy/TURBT/Histology

Biopsies/TURBT will be obtained as part of the cystoscopic procedures. Perform biopsy and resection of all lesions and suspicious areas seen in blue light and white light. Both biopsied and resected tissue will be examined by the local pathologist, then evaluated by independent and blinded central pathologists. Central pathology results will be used as reference standard in the study efficacy endpoints.

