7.2 Secondary Efficacy Endpoint

The secondary efficacy endpoint of this study as below:

- The proportion of patients with one or more CIS lesions detected with Hexvix blue light cystoscopy not by white light cystoscopy.
- The lesion detection rate of Hexvix blue light cystoscopy, compared to white light cystoscopy per lesion type (PUNLMP, CIS, Ta, T1, T2-T4).
- The proportion of false positive lesions detected with Hexvix blue light cystoscopy and white light cystoscopy.

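### The per-lesion-type objective compares blue with white light, but section 10.4.2.2 plans no comparative estimate with an interval.

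*Combined protocol and SAP*

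**What the plan says.** Section 2.2 lists as a secondary objective: "Comparison of detection rates of bladder lesions of Hexvix blue light cystoscopy and white light cystoscopy per lesion type (PUNLMP, CIS, Ta, T1, T2-4"). Section 7.2 gives the matching endpoint: "The lesion detection rate of Hexvix blue light cystoscopy, compared to white light cystoscopy per lesion type". Both are comparative.

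Section 10.4.2.2 sets the analysis: "Secondary efficacy endpoints will be analyzed descriptively, including event rate and 95% confidence intervals based on the FAS and PPS". On the type of interval it adds: "Exact 95% confidence interval will be calculated similarly to that of the primary efficacy endpoint". The method referred to, in section 10.4.2.1, is "an exact test for single proportion, using the cumulative binominal distribution, with a significance level of 0.025 (1-sided) will be used", together with a 95% interval for that one proportion. For intervals built on tissue data, section 10.4.2.2 says: "Bladder biopsy/TURBT data should be assumed to be independent of each other". It also limits the aim: "But no formal statistical inference will be made to the secondary efficacy endpoints".

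On which lesions reach pathology, section 4.3.2.1 says: "Perform biopsy and resection of all lesions and suspicious areas seen in blue light and white light". No sampling of normal-looking mucosa is described.

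Section 10.1 defers detailed methods to a statistical analysis plan to be finalised before the first database lock. No separate text of that plan is in the documents.

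**The concern.** The objective asks how blue compares with white for each lesion type, and the stated method answers a different question: what each rate is on its own. A reader of the final tables could subtract or divide the two point estimates, but would find no interval for the result. An interval that allows for several lesions in one bladder needs patient-level data, so it could not be rebuilt from lesion totals.

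The rates also need a label. A lesion missed by both lights is never sampled, so it cannot enter the denominator. Without a note to that effect, a figure called a detection rate may be taken for sensitivity. The plan does not name the ratio, which is the one contrast that this denominator does not affect.

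**Working it through.** **The plan's own figure.** The only sample-size figure is 94 patients, for the primary endpoint. It reproduces: rejecting at 16 or more of 94 gives a one-sided level of 0.0239 under 10% and a power of 0.8006 under 20%. It says nothing about lesion numbers, and the documents give no lesion counts by type. All counts below are assumed, to show the mechanics.

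**Step 1: what the stated method gives.** Assume 100 lesions of one type: 81 found by both lights, 15 by blue only, 4 by white only.
- Blue: (81 + 15)/100 = 96%, exact 95% interval 90.1 to 98.9.
- White: (81 + 4)/100 = 85%, exact 95% interval 76.5 to 91.4.

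Under the natural reading, these two lines are the whole planned output.

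**Step 2: what the objective needs.**
- Ratio: 96/85 = 1.13.
- Difference: (15 − 4)/100 = 11 points.

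Standard errors if lesions were independent:
- Log ratio: √[(15 + 4)/(96 × 85)] = 0.0483.
- Difference: √[15 + 4 − (15 − 4)²/100]/100 = 0.0422.

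To allow for clustering within patients, multiply each standard error by the square root of a design effect. The documents give none, so a range is shown. The intervals are 1.13 × exp(±1.96 × SE) and 11 ± 1.96 × SE in points.

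| Design effect (assumed) | Ratio, 95% interval | Difference in points, 95% interval |
|---|---|---|
| 1.0 | 1.03 to 1.24 | 2.7 to 19.3 |
| 1.5 | 1.01 to 1.27 | 0.9 to 21.1 |
| 2.0 | 0.99 to 1.29 | −0.7 to 22.7 |

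The contrast needs its own interval, and its width depends on clustering, which section 10.4.2.2 assumes away.

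**Step 3: what can be recovered from the planned tables.** The two intervals alone give no interval for the contrast. If the counts are shown and every lesion was found by at least one light, a careful reader can rebuild the cross-table: blue only = 100 − 85 = 15, white only = 100 − 96 = 4. That yields the first row of the table above and no other, because the spread of lesions over patients is not in the totals.

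**Step 4: the denominator.** Assume true sensitivities of 85% (blue) and 65% (white). Each reported rate is the true rate divided by P(found by either light). How far the misses coincide is unknown, so the full range is shown.

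| Misses | P(either) | Blue | White | Difference | Ratio |
|---|---|---|---|---|---|
| Never coincide | 1 | 85.0% | 65.0% | 20.0 | 1.31 |
| Independent | 1 − 0.15 × 0.35 = 0.9475 | 89.7% | 68.6% | 21.1 | 1.31 |
| Every blue miss is also a white miss | 0.85 | 100% | 76.5% | 23.5 | 1.31 |

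The denominator cancels in the ratio: 0.85/0.65 = 1.31 in every row. The single-light rates and the difference both move with it.

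**The case against.** **The text does not say one interval per light.** True. The primary and CIS endpoints count blue-only findings per patient, so intervals calculated in a similar way could mean a blue-only proportion per lesion type. That reading would still leave out white-only lesions and would not give the two rates that the endpoint names. Either way, the comparison is undefined.

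**The endpoint is descriptive.** Also true, and a stated choice. A ratio or difference with an interval is descriptive too, so nothing here asks for a test.

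**The detail may sit in the statistical analysis plan.** It may, and its absence there cannot be shown. Section 10.4.2.2 promises detailed tabulation, and lesion number, type and location are recorded under each light, so the cross-table can be made. But the protocol commits to neither the cross-table nor a comparative interval.

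**Two stronger readings are tempting.**
- A reader might infer that ignoring the pairing throws away precision. It does not here. With no lesion missed by both lights, the covariance is slightly negative (0.81 − 0.96 × 0.85 = −0.006). The paired interval for the difference, 2.7 to 19.3, is a little wider than an unpaired one, 3.0 to 19.0.
- A reader might infer that the plan will hide a real difference, because the intervals in step 1 overlap while the difference excludes zero for independent lesions. No section tells anyone to judge by overlap, and both point estimates would be visible. The pattern depends on the assumed counts: 18 blue only and 3 white only in 100 lesions gives 91.5 to 99.4 against 73.1 to 89.0, with no overlap. It also depends on independence, since at a design effect of 2 the difference in step 2 no longer excludes zero.

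**Conclusion.** The point holds in a limited form. A comparative secondary objective has no stated comparative estimate with an interval, and the rates it will report are relative to lesions found by either light without being labelled so. The first part rests on the natural, not literal, reading of section 10.4.2.2, and on the absence of any ratio, difference or cross-table elsewhere in the documents. The second rests on the sampling rule in section 4.3.2.1.

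The numerical size cannot be fixed, because the documents give no lesion counts, no clustering figure and no rate of lesions missed by both lights. In the assumed examples, the lower limit for the difference moves from 2.7 to −0.7 points as the design effect goes from 1 to 2. A true 20-point difference is reported as 20.0 to 23.5. The primary conclusion is not affected. The documents do not support a claim that pairing would sharpen the result, or that the plan adopts an overlap rule that loses power.

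**What to change.** In section 10.4.2.2, and in the statistical analysis plan before database lock, specify for each lesion type:

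1. Counts of lesions found by both lights, by blue only, by white only, and in total.
2. The ratio (lesions found by blue divided by lesions found by white) as the main descriptive contrast, with the difference as a supplement.
3. A 95% interval for each that allows for several lesions per patient, for example by resampling patients.
4. A label on the single-light rates and on the difference, stating that they are relative to lesions found by either light.

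Keep the analysis descriptive, with no formal inference. The data are already collected, so the cost is wording and a little programming. Intervals will be wider than under independence and may be unstable for rare lesion types, where counts alone can be shown.

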3. All papillary lesions detected will be resected using TURBT and all flat and suspicious lesions detected will be biopsied. The lesions resected and biopsied should be marked and pathologically examined separately. For patients randomized to undergo blue light cystoscopy and for training patients, the completeness of the resection should always be checked under blue light before finalizing the TURBT procedure until it is ensured that all lesions and suspicious areas are completely resected. Both biopsied and resected tissue will be examined by the local pathologist, then evaluated by independent and blinded central pathologists. Central pathology results will be used as reference standard in the study efficacy endpoints.

Registration of lesions on the bladder chart will include presence of lesion, type (papillary, or flat), number of lesions and location (bladder neck anterior, trigone, around ureteric orifice right, around ureteric orifice left, posterior floor, right lateral wall, cranial wall, left lateral wall, dome, anterior bladder wall and bladder neck posterior).

The cystoscopy will be videotaped, and the video will be used as the source data for the cystoscopy procedure. The cystoscopy video recording of all training subjects (at least 4 subjects) per study site will be reviewed by sponsor for site qualification. After sponsor's written approval, the site can start with cystoscopic examination for randomized subjects.

If assigned investigator and / or sub-investigator failed to fulfil the requirements continuously, more training subjects can be requested and reviewed by the sponsor. It needs to be discussed to see if more trainings can be delivered, or tentatively to evaluate if change of investigator is possible

3) Handling and Interpretation of blue light cystoscopy

When using the blue light cystoscopy, there are several points to consider obtaining the best results. Correct handling of the endoscope is important to optimize the results. False fluorescence may appear and correct interpretation of the fluorescing areas is important.

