7.3 Central Pathology Evaluation

All efficacy endpoints assessment will be based on central pathology consensus panel results to reduce the difference between the pathological evaluations used in the efficacy analysis.

The WHO 2016 World Health Organization/International Society of Urologic Pathology consensus classification and the Union for International Cancer Prevention (UICC) 2017 8th edition of TNM classification for staging of bladder cancer will be used to grade and stage tumors. Two independent pathologists unaware of the diagnosis of the local pathologist and whether the biopsy came from a lesion seen in white light or blue light or both, provide a pathology diagnosis independently. If the two pathologists agree on the diagnosis, this is the final diagnosis. If they disagree, a third independent pathologist will make a diagnosis without knowing the diagnosis of the two first pathologists. If this diagnosis is in agreement with the diagnosis made by the one of the first pathologists, this result will be the final diagnosis. If they agree on a diagnosis, this will be the final consensus diagnosis. If they fail to reach agreement, this lesion will be excluded from the statistical analysis.

A histologically confirmed malignancy is a tumor staged/graded as CIS, Ta, T1 orT2-T 4 by the consensus panel. Lesions can be classified to PUNLMP, low grade and high grade.

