10.1 General Principle

The Statistical Analysis Plan is prepared by the Biostatistician and the Principal Investigator according to the study protocol and will be finalized and documented prior to the first database lock. Detailed statistical analysis methods will also be specified in the statistical analysis plan.

All statistical analyses will be completed using SAS version 9.4 or higher. See statistical analysis plan for specific statistical methods.

Continuous variables will be described by mean, standard deviation, median, first quartile, third quartile, maximum and minimum.

Categorical variables will be described by frequency and percentage. If necessary, 95% confidence interval (95% CI) of the percentage will be calculated.

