10.2 Determination of Sample Size

Approximately 380 subjects will participate in the study and will continue until 94 subjects with pathologically confirmed of bladder cancer at Ta, T1, and CIS stages.

The sample size calculation for this study is as follows:

The primary efficacy endpoint of this study is "The proportion of patients with histology-confirmed tumors (Ta, T1, or CIS) who have at least one such tumor found by Hexvix but not by white light cystoscopy. A proportion of 10% is considered clinically significant, and if the actual proportion is 20%, that is, the null hypothesis is P null hypothesis = 10% and the alternative hypothesis is P alternative hypothesis = 20%, a total of 94 subjects with pathologically confirmed Ta, T1, and CIS stage bladder cancer are required at a one-sided significance level of 0.025 with 80% power based on an exact test for one proportion.

Assuming that 35% of subjects will have bladder cancer after Hexvix-assisted blue light cystoscopy and/or white light cystoscopy, bladder cancer with Ta, T1 and CIS stage accounting for 75%, 359 subjects are expected to be enrolled in this trial. Considering the 5% drop-out rate, a total of about 380 subjects are required. The study will continue until 94 subjects have bladder cancer after Hexvix-assisted blue light cystoscopy and/or white light cystoscopy and are pathologically confirmed as Ta, T1, and CIS stage bladder cancer.

Note: A minimum of 4 subjects included at each center will be training subjects, and those training subjects are in addition to the estimated sample size. Moreover, training subjects are not included in the randomization procedure and efficacy endpoints analysis set, but included in the safety analysis set.

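### Lesion-level 95% confidence intervals must treat all biopsies as independent, so they can cover less than 95% when patients contribute several correlated lesions

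*Combined protocol and SAP*

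**What the plan says.** Section 10.4.2.2 reports each secondary efficacy endpoint as a rate with an interval: "Exact 95% confidence interval will be calculated similarly to that of the primary efficacy endpoint". Where the interval rests on tissue samples, it adds that "Bladder biopsy/TURBT data should be assumed to be independent of each other". The synopsis repeats this under its statistical analysis method. The same section says that "no formal statistical inference will be made to the secondary efficacy endpoints".

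Section 7.2 lists three secondary efficacy endpoints. One counts patients (CIS found only under blue light). Two count lesions: the detection rate under each light by lesion type, and "The proportion of false positive lesions detected with Hexvix blue light cystoscopy and white light cystoscopy".

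Section 4.3.2.1 makes each lesion its own pathology unit: "The lesions resected and biopsied should be marked and pathologically examined separately". Section 1.1 describes bladder tumours as usually multicentric. Section 10.1 defers detail: "Detailed statistical analysis methods will also be specified in the statistical analysis plan". No section names a clustered interval, a GEE or mixed model, a bootstrap, or a sensitivity analysis for lesion-level rates.

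**The concern.** An exact binomial interval on pooled lesions treats every lesion as a separate piece of information. Lesions from one bladder share the patient, the operator, the instillation and the underlying disease. If their results are positively correlated, the effective number of observations is smaller than the lesion count, and an interval labelled 95% covers less than that.

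For the false positive proportion the sign of the correlation follows from the plan's own planning figure. Section 10.2 states: "Assuming that 35% of subjects will have bladder cancer after Hexvix-assisted blue light cystoscopy and/or white light cystoscopy". The other 65% have no bladder cancer, so under Section 7.3 every lesion sampled from them is non-malignant, while patients with cancer contribute at least some true positives. Patient status therefore drives the lesion result.

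Because these endpoints carry no test, the interval is the only statement of uncertainty that the reader gets. False positives are also the main diagnostic cost of blue light, and Section 4.3.2.1 itself warns of false fluorescence. No test or success rule depends on these intervals.

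**Working it through.** **The plan's own figures.** For n = 94, the smallest rejection count with tail probability at most 0.025 under a 10% rate is 16 (actual alpha 0.0239). Power at 20% is 0.8006, and 94 is the smallest n reaching 80%. Enrolment is 94/(0.35 × 0.75) = 358.1, hence 359. Then 359/0.95 = 377.9, against about 380 stated. These reproduce, and they are patient-level. The only figure stated for the lesion-level intervals is the nominal 95%. It holds with one lesion per patient or zero correlation, where simulated coverage with 94 patients is 95.2–96.6%.

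**Inputs from the documents.** 94 patients with Ta, T1 or CIS; 359 subjects; 35% with cancer (Section 10.2); stage shares of 70% Ta, 20% T1 and 10% CIS (Section 1.1). Applied to 94 for illustration, the shares give about 66, 19 and 9 patients.

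**Assumed inputs.** Mean lesions of one type per contributing patient, 1.2 to 4; ICC, 0 to 0.3; true rate, 0.8 or 0.9.

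**Design effect.** With m lesions per patient and correlation ρ, DE = 1 + (E[m²]/E[m] − 1)ρ. Taking m = 1 + Poisson(mean − 1):

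- Mean 2: E[m²] = 1 + 4 = 5, so DE = 1 + (5/2 − 1)(0.3) = 1.45 and √DE = 1.20.
- Mean 3: E[m²] = 2 + 9 = 11, so DE = 1 + (11/3 − 1)(0.3) = 1.80 and √DE = 1.34.

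The naive standard error is therefore 1 − 1/1.20 = 17% to 1 − 1/1.34 = 25% too small.

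**Coverage of the ordered interval, one lesion type, 66 patients** (beta-binomial simulation, 20,000 replicates):

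| Mean lesions / ICC | Rate 0.8 | Rate 0.9 |
|---|---|---|
| 1.5 / 0.1 | 0.955 | 0.960 |
| 1.5 / 0.3 | 0.938 | 0.945 |
| 2 / 0.1 | 0.945 | 0.948 |
| 2 / 0.3 | 0.912 | 0.920 |
| 3 / 0.3 | 0.869 | 0.880 |
| 4 / 0.3 | 0.841 | 0.843 |

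With all 94 patients the results barely move: 0.914 and 0.913 at 2/0.3, 0.868 and 0.874 at 3/0.3, 0.833 and 0.840 at 4/0.3. With 9 or 19 patients, coverage is 95–99% at 1.2–1.5 lesions but 85–90% at 4/0.3. As a cross-check, coverage is roughly 2Φ(1.96/√DE) − 1. For exactly 3 lesions per patient this gives 90.2% at ICC 0.2 (DE 1.4), 87.9% at 0.3 (DE 1.6) and 83.4% at 0.5 (DE 2.0).

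**False positives.** Take a false positive to be a lesion outside the Section 7.3 definition ("A histologically confirmed malignancy is a tumor staged/graded as CIS, Ta, T1" or T2–T4), counted over all lesions seen under that light. Assume that every cancer patient contributes a lesion. Let f be the share of cancer-free patients who contribute one, and q the false positive share within cancer patients. The cancer-free share of contributing patients is π = 0.65f/(0.65f + 0.35). If lesions are independent given cancer status, ICC = π(1 − q)/[π + (1 − π)q], which is positive for any q below 1.

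- f = 0.1, q = 0.3: π = 0.065/0.415 = 0.157, ICC = 0.27.
- f = 0.5, q = 0.2: π = 0.325/0.675 = 0.481, ICC = 0.66.
- f = 1, q = 0.1: π = 0.65, ICC = 0.585/0.685 = 0.85.

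The simulation used 359 subjects, and also 75% of that because the number randomized out of blue light is not given. Over f from 0.1 to 1 and q from 0.1 to 0.3, coverage of the ordered interval by mean lesions (cancer/no cancer) is 89–95% at 1.5/1.2, 84–93% at 2/1.5 and 77–93% at 3/2. At f = 0.5, q = 0.2 and means 2/1.5 it is 0.875–0.879.

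**A patient-clustered alternative.** Apply the exact interval to an effective sample size, that is, lesions divided by an estimated design effect floored at 1. It covers 0.951–0.972 with 66–94 patients and 0.951–0.964 over all 120 false positive cells. In a wider 500-cell check (9 to 94 patients, rates 0.5–0.95) its lowest coverage was 0.927, where the plain interval gave 0.862. With a t adjustment the lowest was 0.938, and it never fell below the plain interval.

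**The case against.** The strongest case is about weight. The endpoints are descriptive, the assumption is declared openly, and no error rate, sample size or success rule changes. That is correct, and it is why the point does not reach the trial's conclusion. It does not repair the coverage of a reported interval.

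The size is also assumed. Describing bladder tumours in general as multicentric does not show that patients in this trial average 3 or 4 lesions of the same type, and for detection rates even the sign of the correlation is an assumption. At low multiplicity the conservatism of the exact method absorbs most or all of the effect, and at a true rate of 0.95 the shortfall is milder (93.0% at 2/0.3). All of this stands. The claim is that intervals can under-cover, not that every one will.

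For false positives, the cap of 0.3 on q has no source in the documents, and vessels or inflammation may fluoresce in cancer patients too. With q = 0.5 and 359 subjects, coverage rises to 93–95%, 90–95% and 87–93% for the three lesion-count settings. The 77% end is a corner case (f = 1, q = 0.1, means 3/2). This shrinks the shortfall but does not change its sign. The documents do not define a false positive or say how PUNLMP counts, so the result depends on the definition used here.

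The 9-patient case for CIS is not the only reading, since Section 1.2.2 cites CIS in 30% and 39% of patients in earlier studies. Finally, detailed methods are left to the SAP, but a SAP that follows the protocol would carry forward a rule the protocol has already fixed.

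**Conclusion.** The concern holds. The plan fixes an independence rule for two lesion-level endpoints, and with positive within-patient correlation that rule gives intervals that are too narrow. The shortfall is nil or small at about 1.5 lesions of a type per patient or at ICC 0.1 with 2 lesions. It is about 3–4 points at 2 lesions and ICC 0.3, and 7–8 points at 3 and 0.3. For false positives the positive sign follows from the 35% planning assumption and the Section 7.3 definition of malignancy, while its size depends on the assumed f, q and lesion counts. This should be corrected, but it does not touch the primary analysis, the 94-patient target or the patient-level CIS endpoint.

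**What to change.** In Section 10.4.2.2 and the synopsis, replace the independence sentence with a statement that 95% intervals for lesion-level rates take the patient as the cluster. One suitable form is the exact interval on an effective sample size: lesions divided by a design effect from the cluster-robust ratio-estimator variance, floored at 1, optionally with a t adjustment on patients minus 1 degrees of freedom.

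Use it for sparse lesion types too, rather than reverting to the plain interval merely because patients are few. Keep the plain exact interval for patient-level endpoints and for observed proportions of 0 or 100%, where the estimated between-patient variance is zero and no design effect can be formed. A percentile bootstrap over patients is an alternative only where patients are many: it covered 0.92–0.95 with 66–94 patients, 0.87–0.92 with 19 and 0.73–0.90 with 9. Print the number of patients and lesions beside each rate.

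The cost is wording, a little programming and wider intervals; no new data or patients are needed. With 66–94 patients the interval is 1–3% wider with no correlation, 8% at 2/0.1, 21% at 2/0.3, 35% at 3/0.3 and 47% at 4/0.3. With 9–19 patients and no correlation it is 3–8% wider, or 4–23% with the t adjustment. The replacement is not guaranteed to reach 95% (lowest found, about 93%). Section 10.1 has the SAP finalized before the first database lock, so the change should be made by then.
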